weeks (2 sessions per week). After pretests, the children were matched age, sex, and level of functioning and then randomized into the 3 groups. A parent orientation was conducted in-person/ through zoom before the training period to introduce the training activities and intervention strategies. Each training session lasted about one hour. All sessions were video recorded for further behavioral coding. The current study was conducted in the midst of the COVID-19 pandemic (between 2019 and 2022). Due to the initial close down and the later restriction of face-to-face (F2F) interaction, we decided to be more pragmatic and used a hybrid clinical trial delivery model (Bhat et al., 2021; Cleffi et al., 2022; Srinivasan et al., 2021; Su et al., 2021). The participating families chose between an F2F or a Telehealth (TH) training delivery method based on their convenience and comfort level of social interactions during the pandemic.

Training Protocols

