Trained testers assessed the training-related changes in motor performance using standardized during each test visit. For the standardized tests, we used the Bruininks-Oseretsky Test of Motor Proficiency (BOT-2) to assess children's gross and fine motor proficiency (Bruininks et al., 2005), a 2-Minute Walk Test (2MWT) to assess their endurance (Bohannon et al., 2018), and the bilateral motor coordination subtests of the Sensory Integration and Praxis Tests (SIPT) to access their praxis performance (Ayres, 1988). Parents also completed the Developmental Coordination Disorder Questionnaire (DCD-Q; Schoemaker et al., 2006) at each test visit, and both parents and the children filled out exit questionnaires to provide feedback on the feasibility, acceptability, and benefits of the interventions

Standardized Tests

Bruininks-Oseretsky Test of Motor Proficiency (BOT-2): BOT-2 is a valid and reliable assessment that targets 4 motor area composites with 8 subscales, including a) Fine Manual Control area, consisting of Fine Motor Precision, Fine Motor Integration subscales; b) Manual Coordination, consisting of Manual Dexterity and Upper-limb Coordination subscales; c) Body Coordination, consisting of Bilateral Coordination and Balance Subscales; and d) Strength and Agility, consisting of Running Speed and Agility and Strength subscales. The standard scores of the four motor areas were used to assess the training-related changes in motor performance.

Two Minute Walk Test (2MWT)

2MWT is a standardized measure of endurance. The child was asked to walk as fast as they can (without running) around 2 cones placed 50-feet apart for 2 minutes. The total distance the child walked in the 2-minute period was used to assess the training-related changes in endurance.

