Sensory Integration and Praxis Tests (SIPT): We used the postural praxis and bilateral motor coordination subtests of the Sensory Integration and Praxis Tests (SIPT-PP and SIPT-BMC) to evaluate the praxis and sensory integration performance in children with ASD (Ayres, 1988). During the SIPT-PP, the tester sat across the children and performed 17 novel postures that involved fingers and upper/lower limb movements. An error was counted if the children posed with insufficient/exaggerated joint angles, incorrect joint and hand orientation, or using the wrong side of the body. Similarly, during the SIPT-BMC test, the tester sat across the children and performed 22 rhythmic action sequences involving hand-tapping, foot-stomping, and foot-tapping. The children were asked to repeat the movement sequences back to the tester. An error was counted if the child paused in between the movement sequence, couldn't pick up the rhythm, moved too fast or too slow, or failed to perform the right movement sequences. The number of errors the children made during the SIPT-PP and SIPT-BMC tests were used to monitor the training-related changes in praxis performance.

Executive functioning (EF) Task

During the EF task, we will use e-versions of variations of the Flanker test to assess the inhibition control and cognitive shifting elements of EF. There will be 2 conditions in the Flanker task, including: a) Congruent: Five fishes facing in the same direction (left or right) will be presented, and the child will be asked to raise the left or right index finger depending on the direction in which all the fishes are facing, b) Incongruent: the child will be presented with 4 fishes facing the same direction while the center fish will be facing in the opposite direction. Children will be asked to point to the left or right index finger depending on the direction of the center fish.

Drumming Synchrony Task

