Study Title: The Effect of Play on Social and Motor Skills of Children With ASD

NCT #: NCT04258254

Date: 06/01/2020

Statistical Plan

Outcome measures will be obtained at the pretest and posttest. The BOT standardized motor test offers a fine-motor (precision+integration), gross motor coordination, agility and strength scores. The SIPT standardized praxis subtests provides praxis errors. t-tests or Repeated Measures ANOVA will be used to compare scores between post and pretests.

Post-intervention, the multimodal group will show improvements in the standard motor coordination variables, compared to their own baseline and compared to the control group. Specifically, we expect to see improved gross motor scores, fewer praxis errors as well as greater spontaneous verbalization in the multimodal group compared to the general movement or control group. In terms of fNIRS activation data, we expect greater multiregional activation in the multimodal group during the post-test compared to their own baseline. We expect fewer changes in activation or more localized activation in the general movement or control group.

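### The SAP predicts between-group advantages but names no primary outcome, primary contrast, alpha, error control or success rule, so the false-positive risk depends on a rule chosen later

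*SAP*

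**What the plan says.** The Statistical Plan contains one sentence on method: "t-tests or Repeated Measures ANOVA will be used to compare scores between post and pretests". It describes change over time, leaves the choice of method open, and specifies no test between arms.

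The next paragraph predicts differences between arms. It first expects the multimodal group to improve "compared to their own baseline and compared to the control group", which names one comparator. It then expects "improved gross motor scores, fewer praxis errors as well as greater spontaneous verbalization in the multimodal group compared to the general movement or control group", which names two comparators and three domains.

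None of the three domains is tied to a single score:

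- **Gross motor.** The SAP writes "The BOT standardized motor test offers a fine-motor (precision+integration), gross motor coordination, agility and strength scores". The Protocol (Standardized Tests, BOT-2) lists four composites, none of them called gross motor, and says "The standard scores of the four motor areas were used to assess the training-related changes in motor performance".
- **Praxis errors.** The Protocol has two counts: "The number of errors the children made during the SIPT-PP and SIPT-BMC tests were used to monitor" change.
- **Spontaneous verbalization.** The Protocol defines no measure. The nearest text, under Experimental Procedures, is "All sessions were video recorded for further behavioral coding".

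Neither document states a primary outcome, a primary contrast, an alpha or its sidedness, a multiplicity procedure, an omnibus gate, or how many favourable results would support the hypothesis. The text shows no sign of redaction at these points.

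**The concern.** A reader of the results cannot tell which comparison was the planned test. With several domains, two comparators joined by an unexplained *or*, and more than one candidate score in two of the domains, a favourable result in any one place could be presented as the predicted finding. A single planned two-sided 5% test wrongly favours the multimodal group 2.5% of the time. If any one of several tests will do, that chance rises, and the documents do not limit how far.

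**Working it through.** The documents give no alpha, power or sample-size calculation, so there is no figure of the plan's own to reproduce. The check asks how far the false-favourable chance moves across decision rules that the text leaves open.

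**From the documents.** 45 children and 3 arms (Protocol, Participants); three domains and up to two comparators (SAP).

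**Assumed.** Equal arms, 45/3 = 15; independent children; two-sided 5% per test, so 2.5% in the predicted direction; correlation between outcomes of 0 to 0.7; no true difference anywhere.

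**Bounds for six comparisons (3 × 2).** The sum bound is 6 × 0.025 = 15%. Six independent tests would give 1 − 0.975^6 = 14.1%. The true figure is lower because both contrasts share the multimodal arm and the outcomes are correlated.

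**Simulation.** Normal outcomes, separate two-sample t-tests (28 df), at least 100,000 trials per setting. The gate is an F-test on 2 and 42 df for each outcome. Chance of a false favourable claim:

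| Rule for claiming support | Correlation 0 | Correlation 0.7 |
|---|---|---|
| One planned test | 2.5% | 2.5% |
| Any of six: three domains, two comparators | 13.1% | 9.7% |
| Any of four: verbalization left out | 8.9% | 7.5% |
| Any of three: control only | 7.2% | 5.5% |
| Any of six, omnibus gate per outcome | 6.1% | 4.8% |
| Any of three: control only, with that gate | 3.6% | 2.9% |
| Both arms beaten on the same outcome | 1.4% | 1.1% |
| Any of twelve: six scores tested separately | 24% | 14% |

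The six scores in the last row are the three BOT-2 composites other than Fine Manual Control, the two SIPT counts, and verbalization. Treating all three composites as gross motor is a choice made for this check. Manual Coordination, for one, includes Manual Dexterity.

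Replacing the t-tests by ANCOVA on the pretest score (assumed pre-post correlation 0.6) leaves the six-comparison row nearly unchanged, at 13.3% to 9.9%. Within-group, fNIRS and follow-up tests are not counted.

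**Power of a single primary test.** Assume a true difference of 0.8 SD. With 15 per arm the noncentrality is 0.8 × √(15/2) = 2.19, which on 28 df gives 56% power. ANCOVA divides this by √(1 − r²), where r is the pre-post correlation:

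- r = 0.5: 2.19/0.866 = 2.53, power 68%.
- r = 0.7: 2.19/0.714 = 3.07, power 84%.

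**The case against.** The strongest reply is that the six tests are not in the SAP. Its only method sentence is pre-post, and the between-group statements are expectations, not a success rule. A reader might infer that the plan has a 10% to 13% false-positive rate. The documents do not support that: it is one reading among several. The sentence that names only the control group gives 7% to 5.5%. If the Repeated Measures ANOVA were used as a gate as well, that falls to 3.6% to 2.9%, close to the 2.5% benchmark. This part of the reply stands, and it is why the size is given as a range by rule. It does not remove the omission, because nothing in either document selects among the rules.

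A reader might likewise take 24% as the exposure. It needs zero correlation among six scores, three of them from one instrument, and is 14% at correlation 0.7.

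The figures also treat the arms as independent. The Protocol says children were matched before randomization but does not say that matched sets were formed. If they were, unpaired tests on posttest scores are conservative. At an assumed within-set correlation of 0.3, the six-comparison figure is 4.7% to 5.9%. The single-test figure also drops, to about 1.1%, so the relative inflation remains.

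Finally, the Protocol describes conduct up to 2022 in the past tense, so the time for naming a primary test may have passed. That limits the remedy, not the finding. A reader might go further and infer that outcomes were selected after the results were seen. Neither document reports results or says whether data have been examined, so that inference has no support here.

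**Conclusion.** The omission is certain: no primary outcome, primary between-group comparison, alpha, error control or success rule appears in either document. Its numerical size is not fixed by the plan. Under the stated assumptions the false-favourable chance runs from about 1% (both arms beaten on one outcome) to about 13% (any of six comparisons at zero correlation), against 2.5% for one planned test. It goes higher only if several scores per domain are tested separately. Confidence is high for the omission; the percentages are illustrations conditional on the rule. This should be corrected because it governs how every between-group claim from the trial is read.

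**What to change.** **If outcome data have not been examined:**

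1. Name one primary test: one BOT-2 composite chosen by the sponsor, posttest score, ANCOVA with the pretest score as covariate, multimodal versus control, two-sided 5%.
2. Replace the two-comparator *or* with a short fixed sequence, one score and one contrast per step, each at two-sided 5%, stopping at the first non-significant step. For example: the primary test; then one named SIPT count versus control; then the primary score versus general movement.
3. Label all other tests exploratory, including verbalization unless a measure is defined for it.

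Under the same null, the sequence keeps the false-favourable chance at 2.5%.

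**If outcome data have been examined:** a primary test named now would be post hoc. Report all between-group results as exploratory and state the full number of tests.

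**Cost.** This changes SAP wording only. Results outside the sequence are not confirmatory. Power for the primary test is modest: about 56% unadjusted, or 68% to 84% with ANCOVA, for the assumed 0.8 SD difference and pre-post correlation of 0.5 to 0.7.

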Study Title: The Effect of Play on Social and Motor Skills of Children With ASD

NCT #: NCT04258254

Date: 06/01/2020

Study Protocol

Participants

45 children with ASD aged between 5 and 15 years were recruited through fliers distributed to local schools, ASD services, advocacy groups, as well as Simons Powering Autism Research (SPARK) participant-research matching service (<https://www.sfari.org/resource/spark/>). We interviewed the potential participants to gather their demographic information (i.e., age, sex, ethnicity), and to confirm their eligibility for participation. Children were included in the study if they had formal ASD diagnoses that were confirmed through a school record (e.g., school psychologist record confirming an ASD diagnosis) and/or an Individualized Education Plan for ASD-related services or a medical or neuropsychological record from a psychiatrist or clinical psychologist using the Autism Diagnostic Observation Schedule (ADOS) and/or Autism Diagnostic Interview-Revised (ADI-R) measures. We additionally used the Social Communication Questionnaire (SCQ) as a screener for ASD symptoms (Rutter et al., 2003). Children were excluded if they have limited comprehension of one-step simple instruction and/or could not complete the pretests due to behavioral issues. Parents of the children completed the Vineland Adaptive Behavioral Scales-2nd edition (VABS; Sparrow et al., 2005), and the Social Responsive Scale questionnaire (SRS; Constantino et al., 2000) to assess the child's adaptive functions and social responsiveness. Following enrollment, children were matched on age, sex, and level of functioning then randomly allocated to the 3 intervention arms. The study procedures were carried out according to the Declaration of Helsinki and were approved by the University of Delaware Institutional Review Board (UD IRB, Study Approval #: 1539736-5). Written informed consent of study participation was obtained from the parent, and a written/verbal assent was obtained from the participating children.

Experimental Procedures

This study includes 3 pretests, 3 posttests, and 16 training sessions conducted over 10 weeks. Eight weeks later a follow-up test was also completed. Specifically, the pretests and posttests were conducted during the first and the last week of the study, while the training sessions were provided during the intermediate 8

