During the drumming synchrony task, children will be seated with a drum placed on the table in front of them. There will be 3 conditions: a) Music: the child will be asked to drum in order to match up to rhythmic beats played aloud in the background, b) Social: the child will sit face to face with an adult and be asked to match up to the movements of the adult. C) Virtual Social: the child will be seated facing a laptop screen and drum with a virtual partner through zoom conferencing. Both the child and the virtual partner will drum to rhythmic beats played aloud in the background.

Parent reported motor outcome using the Developmental Coordination Disorder Questionnaire (DCD-Q)

DCD-Q is a parent questionnaire to screen for developmental coordination disorder in children. Specifically, it screens for the child's performance in three components, Control during movement (motor control while the child is moving or the target object is in motion, ex: catching, throwing), Fine motor/Handwriting (fine motor skills, ex: writing fast and legibly), and General coordination (motor planning/learning, ex: like sports and learn new skills).

Children's survey feedback

Upon finishing all training sessions, each child answered 3 questions to provide feedback on their training experience. The questions include: A) Did you enjoy the activities we did? B) Did you find the activities easy or hard, C) Will you practice similar activities on your own or with mom/dad? Each question was answered with a picture-assisted 5-point Likert score (5- definitely yes/ very easy 😊; 4- yes/easy 😃; 3- maybe, neither too easy nor too hard 😐; 2- not so much/hard 😔; 1- not at all/very hard 😞).

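### The fNIRS hypothesis is judged by separate pre-to-post results within each arm, with no between-arm test of change, and the protocol describes no fNIRS recording

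*SAP*

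**What the plan says.** The SAP's Statistical Plan gives two sentences to fNIRS. For the multimodal arm: "we expect greater multiregional activation in the multimodal group during the post-test compared to their own baseline". For the other arms: "We expect fewer changes in activation or more localized activation in the general movement or control group". No regions, activation measure, scoring rule or between-arm test is given for this outcome.

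The only analysis named anywhere is general: "t-tests or Repeated Measures ANOVA will be used to compare scores between post and pretests". No group-by-time term is mentioned. The motor variables are treated differently, since improvement there is to be shown "compared to their own baseline and compared to the control group".

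The protocol's Testing Protocol and the sections after it describe the BOT-2, the 2-Minute Walk Test, two SIPT subtests, a Flanker task, a drumming task in three conditions, the DCD-Q and feedback questionnaires. The two computer or laboratory tasks open with "During the EF task, we will use e-versions of variations of the Flanker test" and "During the drumming synchrony task, children will be seated with a drum placed on the table in front of them". Neither section mentions brain recording, and fNIRS appears nowhere in the protocol.

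**The concern.** A significant change in one arm and a non-significant or smaller-looking change in another is not evidence that the two changes differ. With about 15 children per arm, within-arm results vary widely by chance, so arms with the same true change will often look different.

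The wording for the comparison arms adds latitude. Fewer changes or more localized activation would each count, in the general movement or the control arm, so several patterns can be read as support. At stake is any claim that multimodal training has a distinct effect on brain activation. That claim could rest on chance differences between three separate pre-to-post analyses.

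The second gap is that a reader of the protocol cannot tell which task's activation is meant, or when it was recorded.

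**Working it through.** The documents give no power, alpha, effect size or SD for fNIRS, so there is no figure of theirs to reproduce. What follows is an illustration.

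**Inputs from the documents.** The total is 45 ("45 children with ASD aged between 5 and 15 years were recruited") and there are three arms ("children were matched on age, sex, and level of functioning then randomly allocated to the 3 intervention arms"). No ratio is stated; an equal split gives 45/3 = 15 per arm.

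**Assumptions not in the documents.** There are 4 to 10 regions, with between-region correlation ρ of 0.3 to 0.6. The true pre-to-post change is the same in all arms, at 0, 0.3 or 0.5 SD of the change. The two-sided level is 5%, uncorrected for the number of regions, and only increases count. The simulation used 8,000 trials per setting.

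**1. Regions scored by significance.** Each region is tested within each arm by a paired t-test, and significant regions are counted. Multimodal has strictly more than both other arms in:
- 22% to 29% of trials when all arms change equally by 0.3 to 0.5 SD;
- 6% to 14% when no arm changes.

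Power per region within an arm of 15 is only 19% at 0.3 SD and 44% at 0.5 SD, so the counts are unstable. A Bonferroni correction over regions lowers the no-change rate to about 2% but leaves 14% to 25% under equal change.

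**2. One continuous measure, averaged over regions.** If each arm has the same probability p of a significant increase, multimodal is significant and control is not with probability p(1 − p). The standardized change of the average over R regions is d/√(ρ + (1 − ρ)/R).
- d = 0.5, ρ = 0.3, R = 10: 0.5/√0.37 = 0.82, p = 0.84, and 0.84 × 0.16 = 0.13.
- d = 0.3, ρ = 0.3, R = 8: 0.3/√0.3875 = 0.48, p = 0.41, and 0.41 × 0.59 = 0.24.
- No change: 0.025 × 0.975 = 0.024.

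The range is about 13% to 24% under equal change and 2% to 3% with none.

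**3. Direct test.** A two-sample test of the averaged change, multimodal against control, is significant in favour of multimodal in about 2% to 3% of trials, whether or not the arms change.

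**4. Where the excess comes from.** Steps 2 and 3 use the same averaged measure and differ only in whether the arms are compared directly. The excess therefore comes from the missing between-arm test and does not depend on counting regions. Ranking the averaged means with no test makes the same point: multimodal comes first in about one third of trials, by symmetry.

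**5. Power of the direct test at 15 per arm.** By the normal approximation, power = Φ(d/√(2/15) − 1.96), with √(2/15) = 0.365 and d the between-arm difference in SDs of change.
- d = 0.5: Φ(1.369 − 1.96) = 28%.
- d = 0.8: Φ(2.191 − 1.96) = 59%.

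For 80% power, n per arm = 2(1.96 + 0.842)²/d², which gives 63 and 25 respectively.

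**The case against.** The strongest reply is that the SAP sets no counting rule. It states an expectation, and greater activation could mean larger amplitude over several regions, which is continuous and could be analysed by the methods the SAP names. A reader might infer that the SAP has chosen to count regions passing a significance threshold. The documents do not say so, and the 22% to 29% range applies only under that reading. This part of the objection stands. It does not rescue the plan, because the averaged continuous measure in step 2 of the working has the same fault.

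A repeated-measures ANOVA could also include a group-by-time term. It could, but the SAP describes its analysis as comparing post with pre, offers t-tests as an alternative, and asks for a control comparison only in the motor sentence.

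The chance effect is symmetric and could favour any arm. That is true, but only a lead for multimodal matches the stated prediction.

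A reader might also infer from the protocol's silence that no fNIRS was recorded and that the hypothesis cannot be tested at all. The documents do not support this. The SAP presupposes fNIRS data, so incomplete description is at least as plausible as absence. The Flanker and drumming tasks are both possible settings, and nothing links fNIRS to either. Taken alone, this gap would be missing detail.

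**Conclusion.** The concern holds in this form: the fNIRS hypothesis rests on a within-arm change set beside loosely described within-arm patterns in the other arms, without the between-arm comparison that the motor outcomes receive.

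Under equal true change of 0.3 to 0.5 SD, such a comparison favours multimodal in roughly 13% to 29% of trials, depending on scoring, against about 2% to 3% for a direct test. With no change in any arm the excess is smaller: 6% to 14% if regions are counted without correction, and none with a single averaged measure (2% to 3%). The sizes rest on an equal split, the assumed region numbers, correlations and effect sizes, and an uncorrected 5% level. The logical point does not depend on them.

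The missing description of fNIRS recording is a separate and secondary gap, which the sponsor can close.

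**What to change.** In the SAP's Statistical Plan, state that the fNIRS hypothesis is judged by the between-arm difference in pre-to-post change in a continuous activation measure over pre-specified regions. The contrasts are multimodal versus control and multimodal versus general movement. Use the group-by-time term of the repeated-measures ANOVA, and report each contrast with a confidence interval. If the spatial claim is to be kept, add a group-by-time-by-region term. Treat multiregional, fewer or more localized patterns as descriptive.

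In the Testing Protocol, name the task during which fNIRS was actually recorded at pretest and posttest. If it was not recorded, remove the fNIRS hypothesis. The protocol reports recruitment and much of the conduct in the past tense, so this sentence can only document what was done.

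The cost is wording, with no new procedure if the recordings exist. The real downside is power: at about 15 per arm the direct contrast has roughly 28% power at d = 0.5 and 59% at d = 0.8, so the between-arm estimate will usually be imprecise and the mechanism claim should be modest.
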